5.3 Subgroup analyses

The primary and secondary endpoint will be analysed in the following subgroups:

- Type of infection: early and delayed.
- Type of fracture: open (Gustilo and Anderson classification) or closed.
- Type of osteosynthesis material: endomedullary nail or needle, plates or screws.
- According to the etiology of the infection: infections by different microorganisms, infections by multidrug-resistant microorganisms.

- According to type of patient: comorbidities, elderly, renal insufficiency, gender.

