1. INTRODUCTION

This is the Statistical Analysis Plan (SAP) for the “DURATION” trial, a multicenter, non-inferiority, open labelled, pragmatic randomized clinical trial comparing different durations of antibiotic therapy in infection of osteosynthesis material (IOM) implanted after long bone fractures and treated with debridement and material retention.

This SAP was developed before the initiation of the study.

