5. STATISTICAL ANALYSIS

5.1 Primary endpoint

The primary endpoint will be collected as a dichotomous variable (yes/no). The primary analysis will be the absolute difference in the proportion of patients reaching the composited primary outcome variable “cure” in the study arms (with one-sided 95% confidence interval) in the ITT population, with the long antibiotic treatment as the reference group. The specific reasons for not reaching overall success (failure, withdrawals, death, etc.) will be specified in both study arms.

A secondary analyses will include subgroups analysis for the primary outcome using the same procedure, and the comparison of the composite variable components (clinical cure, radiological healing and soft tissue coverage) in the PP and CEP, after excluding incorrectly assigned patients.

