5.4 Multivariate analysis

A multivariate analysis will be performed in order to control the potential residual effect of variables other than duration of antibiotic therapy on the primary outcome by logistic regression. Potential confounders will be identified by bivariate analysis of their associations with the primary outcome, considering a p value <0.15 , and will be entered into the multivariate model to check if the effect of the duration of therapy is significantly modified. Expected potential confounders include age, Charlson, delay in DAIR, type and location of fracture, type of osteosynthesis material, microorganism, and antibiotic group. The effect of study sites will be explored by classifying the sites as those with higher and lower cure rates, and including it as a potential confounder.

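### Subgroups of the primary outcome reuse the one-sided non-inferiority interval and no interaction is planned, so the analysis cannot show whether the effect of duration differs between them

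*SAP*

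**What the plan says.** The introduction describes "a multicenter, non-inferiority, open labelled, pragmatic randomized clinical trial comparing different durations of antibiotic therapy". Section 5.1 sets the primary analysis as the absolute difference in the proportion cured, "with one-sided 95% confidence interval) in the ITT population, with the long antibiotic treatment as the reference group". It continues: "A secondary analyses will include subgroups analysis for the primary outcome using the same procedure".

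Section 5.3 gives the scope: "The primary and secondary endpoint will be analysed in the following subgroups". Its five bullets hold about nine factors: infection type ("Type of infection: early and delayed"), fracture type, osteosynthesis material, microorganism, multidrug resistance, and four patient factors ("According to type of patient: comorbidities, elderly, renal insufficiency, gender").

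The nearest text to a check for effect modification is in section 5.4, where covariates associated with the outcome at p<0.15 "will be entered into the multivariate model to check if the effect of the duration of therapy is significantly modified". No treatment-by-subgroup term is named there, and the section does not refer to the subgroups of 5.3. The SAP has no statement that subgroup results are exploratory or are not to be set against the margin.

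**The concern.** A subgroup analysis should ask whether the effect of treatment duration differs between kinds of patient. A one-sided interval computed separately in each subgroup asks whether that subgroup could support non-inferiority on its own. Two subgroups with the same estimated difference can fall on opposite sides of the margin only because one is smaller.

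In a non-inferiority trial, a one-sided bound invites comparison with the margin. A size-driven miss may then be taken as a sign that the short regimen is not supported in those patients, and a pass as a sign that it is. Neither is evidence of a differential effect. The interpretation of the subgroups is at stake, not the main result.

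**Working it through.** **Figures in the plan.** The SAP gives no sample size, margin, power or expected cure rate, so there is no figure to reproduce. These may stand in the protocol, and their absence is not held against the SAP.

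**Inputs.**
- One-sided 95% interval for the absolute difference: SAP section 5.1.
- Assumed: 1:1 allocation overall and within subgroups, no true difference in any subgroup, overall power of 80% or 90%.
- Normal quantiles: z(0.95) = 1.645, z(0.80) = 0.842, z(0.90) = 1.282.

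**Formula.** Let SE be the standard error of the overall difference and M the margin. Sizing for the stated power at zero difference gives M/SE = z(0.95) + z(power), which is 2.486 at 80% and 2.926 at 90%. A subgroup with share s of the patients has standard error SE/√s. It fails to exclude the margin with probability

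1 − Φ((M/SE)·√s − 1.645).

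Margin and cure rate cancel out, so only power and share matter.

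**Results.**

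| Share of patients | 80% overall power | 90% overall power |
|---|---|---|
| one half | 1 − Φ(0.113) = 45% | 1 − Φ(0.424) = 34% |
| one quarter | 1 − Φ(−0.402) = 66% | 1 − Φ(−0.182) = 57% |
| one tenth | 1 − Φ(−0.859) = 80% | 1 − Φ(−0.719) = 76% |

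For a factor that splits the patients into two equal halves, the chance that at least one half misses is 1 − 0.545² = 70% at 80% power and 1 − 0.664² = 56% at 90% power, although the effect is the same in both.

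**What an interaction would do.** With a uniform effect, a test at 0.05 gives a false signal in 5% of trials for each factor. For nine independent tests without adjustment, the chance of at least one is 1 − 0.95⁹ = 37%. For five (one per bullet) it is 1 − 0.95⁵ = 23%.

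Its precision is limited. For two equal halves the difference between the two risk differences has standard error 2·SE, so its two-sided 95% half-width is 1.96 × 2·SE. In units of the margin this is 3.92/2.486 = 1.58 at 80% power and 3.92/2.926 = 1.34 at 90%.

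**Section 5.4.** Entering covariates into a logistic model changes what the duration effect is adjusted for. Without a product term between duration and the covariate, the model still fits one common effect (on the odds-ratio scale), so it cannot show that the effect differs between subgroups.

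**The case against.** The strongest objection concerns infection type. Section 1.1 gives early and delayed infection separate hypotheses and comparisons: 8 against 12 weeks in early infection, and 12 weeks against treatment until healing or implant removal in delayed infection. Whether the short regimen holds up within each is a stated question, and an interaction across them contrasts two different interventions. This stands. A reader might infer that no non-inferiority statement should be made in any subgroup, but section 1.1 does not support that for these two strata.

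Second, the SAP states no pass-or-fail rule for subgroups and places them among secondary analyses. The pass-or-fail reading is therefore a foreseeable use of a one-sided bound, not a rule in the text. This also stands. It does not remove the central gap, since no planned analysis estimates the difference in effect between subgroups.

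Third, reuse of the primary procedure is specified for the primary outcome only. For secondary endpoints, section 5.2 mixes one-sided intervals, 95% intervals of unstated sidedness, risk ratios and tests on medians. The non-inferiority argument should not be carried over to them.

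Fourth, an interaction plan may exist in the protocol, which is not shown. If so, the SAP should refer to it.

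**Conclusion.** The point holds as a minor one, for the primary endpoint. The planned subgroup method does not address whether the effect of duration differs, and section 5.4 does not fill the gap. With no true difference and 80–90% overall power, a subgroup misses the margin with probability about 34–45% at half the patients and 57–66% at a quarter. These figures do not depend on the margin or the cure rate, but they do depend on the assumed power and on equal allocation within the subgroup.

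The documents do not support two stronger readings. One is a specific percentage of trials in which some subgroup, over all factors, would miss the margin. That depends on the sample size or power, subgroup shares and overlap between factors, none of which the SAP gives. The other is that the primary conclusion is compromised. The mechanism is loss of power in small subgroups, and the ITT comparison is untouched.

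**What to change.** In sections 5.1 and 5.3, for the primary endpoint:

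- Replace the instruction to reuse the primary procedure with an estimate of the treatment-by-subgroup interaction on the risk-difference scale, with its two-sided 95% interval.
- Show the subgroup differences with two-sided 95% intervals in a forest plot.
- State that subgroups other than infection type are exploratory and not judged against the margin.
- Treat early and delayed infection separately: report the estimate and interval in each stratum, and say in advance whether a conclusion specific to each is intended.
- In section 5.4, make clear that the model is covariate adjustment and not the check for effect modification.

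The cost is a few sentences and little programming, and fewer subgroup claims can be made. Interaction tests have low power, so a non-significant one does not prove that the effect is uniform. About nine unadjusted tests still leave roughly a 37% chance of at least one false signal if they are independent, and the SAP should acknowledge this where the results are to be interpreted.

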5.4 Multivariate analysis

A multivariate analysis will be performed in order to control the potential residual effect of variables other than duration of antibiotic therapy on the primary outcome by logistic regression. Potential confounders will be identified by bivariate analysis of their associations with the primary outcome, considering a p value <0.15 , and will be entered into the multivariate model to check if the effect of the duration of therapy is significantly modified. Expected potential confounders include age, Charlson, delay in DAIR, type and location of fracture, type of osteosynthesis material, microorganism, and antibiotic group. The effect of study sites will be explored by classifying the sites as those with higher and lower cure rates, and including it as a potential confounder.

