2. STUDY POPULATIONS

The populations for analysis will be:

2.1 Intent-to-treat (ITT) population (ITT): all appropriately-included and randomized patients.

2.2 Per protocol population (PP): all patients who received the complete antibiotic treatment regimen according to the inclusion group.

2.4 Clinically evaluable population (CEP): all patients with evaluation of success at the test of cure at 12 months after completion of treatment, or who have clinical failure before TOC.

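### The adjusted logistic analysis in SAP 5.4 has no stated effect measure, and a shift in its odds ratio would show neither confounding nor a change in the absolute difference of 5.1

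*SAP*

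**What the plan says.** SAP section 1 describes the trial as "a multicenter, non-inferiority, open labelled, pragmatic randomized clinical trial". Section 5.1 fixes the scale of the primary result: "The primary analysis will be the absolute difference in the proportion of patients reaching the composited primary outcome variable" cure, "with one-sided 95% confidence interval", in the ITT population (section 2: "all appropriately-included and randomized patients"), with long treatment as the reference.

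Section 5.4 adds an adjusted analysis. Its purpose is to control for "variables other than duration of antibiotic therapy on the primary outcome by logistic regression". The selection rule is: "Potential confounders will be identified by bivariate analysis of their associations with the primary outcome", at p < 0.15. The selected variables "will be entered into the multivariate model to check if the effect of the duration of therapy is significantly modified". Candidates named in advance include age, Charlson, delay in DAIR, fracture and implant type, microorganism and antibiotic group. Study site is handled by "classifying the sites as those with higher and lower cure rates, and including it as a potential confounder".

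Section 5.4 does not name the effect measure to be reported from the model, does not link it to the absolute difference, and does not say what would count as a modified effect.

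**The concern.** Three features of 5.4 combine badly.

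- **Scale.** The treatment coefficient of a logistic model is a log odds ratio conditional on the covariates. The odds ratio is non-collapsible: averaging patients with different prognosis pulls the population odds ratio towards 1, so conditioning on prognosis moves it away from 1. This needs no imbalance between arms.
- **Selection.** Covariates enter because they predict cure, not because they differ between arms. Predicting cure is the property that moves the odds ratio. Sites grouped by observed cure rate predict the outcome by construction.
- **Reading rule.** The analysis is read by whether the duration effect changes. Randomisation removes confounding by baseline variables in expectation, so a change is most naturally a property of the odds ratio or chance.

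At stake is the interpretation of a supportive analysis. A reader could take a shifted odds ratio as residual confounding of the primary result, or try to judge non-inferiority from a coefficient that is not an absolute difference.

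**Working it through.** **Inputs.** From the SAP: the absolute difference as primary measure (5.1), randomised allocation (sections 1 and 2), and the logistic model with its outcome-based screen (5.4). The SAP gives no cure rate, sample size, allocation ratio or margin, so there is no planned figure to reproduce. Assumed here: 1:1 allocation; cure rates as shown; a normal prognostic score z with SD s on the logit scale, distributed identically in both arms (zero confounding). Differences are short minus long.

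**1. Adjusted versus unadjusted odds ratio.** For each s, find a and b such that the average of expit(a + s·z) equals the long-arm cure rate and the average of expit(b + s·z) equals the short-arm rate, with z standard normal. The adjusted OR is exp(b − a). The unadjusted OR is the ratio of the overall odds; for 80% versus 70% it is (0.70/0.30)/(0.80/0.20) = 0.583.

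| Cure, long vs short | Unadjusted OR | s = 0.5 | s = 1 | s = 1.5 | s = 2 |
|---|---|---|---|---|---|
| 80% vs 80% | 1.000 | 1.000 | 1.000 | 1.000 | 1.000 |
| 80% vs 75% | 0.750 | 0.741 | 0.715 | 0.680 | 0.640 |
| 80% vs 70% | 0.583 | 0.569 | 0.532 | 0.483 | 0.430 |
| 90% vs 80% | 0.444 | 0.433 | 0.401 | 0.355 | 0.305 |

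The shift is systematic whenever the arms differ, grows with prognostic strength, and is zero at a true OR of 1.

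**2. A check by hand.** Take two equal strata, perfectly balanced, with long-arm cure 95% and 65% and OR 0.50 in each.

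- Short-arm odds are 19 × 0.5 = 9.5 and 1.857 × 0.5 = 0.929, so cure is 90.5% and 48.1%, on average 69.3%.
- The overall OR is (0.693/0.307)/(0.80/0.20) = 0.565, not 0.50.
- The stratum differences are −4.5 and −16.9 points. Their mean equals the overall difference, −10.7 points. The risk difference does not drift.

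**3. From odds ratio to points.** An OR of 0.60 means −12.6, −11.7, −9.4 or −5.6 points for patients whose long-arm cure probability is 60%, 70%, 80% or 90%. Nor may an adjusted OR be applied to the overall cure rate. At 80% versus 70% and s = 1.5 the adjusted OR is 0.483; multiplying the overall odds gives 4 × 0.483 = 1.932, or 1.932/2.932 = 65.9% cure and −14.1 points, although the true difference is −10.

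**4. Simulation.** 1000 trials per setting, 150 per arm, s = 1.5. The 10% threshold for a shift is mine; the SAP sets none.

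| Cure | Mean OR, unadjusted → adjusted | Trials with OR shift > 10% | Mean risk difference, unadjusted → standardised | Its SD (points) |
|---|---|---|---|---|
| 80% vs 70% | 0.583 → 0.483 | 71.8% | −9.85 → −9.79 points | 5.0 → 4.3 |
| 80% vs 80% | 0.991 → 0.991 | 56.3% | −0.12 → −0.07 points | 4.6 → 4.0 |

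Odds ratios are exponentiated mean log odds ratios. In the second row there is no average shift; individual trials move by chance alone. The standardised risk difference from the same model stays in place and is more precise.

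**5. Size against sampling error.** At 80% versus 70% and 150 per arm, the standard error of the unadjusted log OR is √(1/(150·0.8·0.2) + 1/(150·0.7·0.3)) = √(0.0417 + 0.0317) = 0.271. The systematic shift is ln(0.583/0.532) = 0.092 at s = 1, about a third of a standard error, and ln(0.583/0.483) = 0.188 at s = 1.5, about 0.7 of one.

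**The case against.** The strongest reply has four parts.

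- **The SAP does not prescribe a comparison of odds ratios.** This stands. Section 5.4 never uses the term and sets no threshold. Its wording could also mean checking whether the duration effect gains or loses significance. A reader might infer a formal before-and-after test of odds ratios, and the text does not go that far. What it does fix is a logistic model with no stated effect measure, read by whether the effect changes.
- **The shift vanishes under the trial's own hypothesis.** This also stands: under equal effectiveness (section 1.1) there is no systematic movement. But the systematic shift then appears when the arms differ, which is when non-inferiority is in doubt, and at the null chance alone moves the odds ratio in many trials.
- **The shift is modest unless covariates are strongly prognostic.** This stands as a limit on size, as step 5 shows.
- **The model can be read on the absolute scale.** True. A reader might infer that the adjusted analysis is useless. It is not: the same model yields a risk difference by standardisation. The gap is that 5.4 does not ask for it.

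Two further readings lack support. Section 5.4 has no decision rule, so it cannot overturn 5.1. Nor does the shift favour non-inferiority: if short treatment is worse, the adjusted odds ratio makes it look worse still.

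**Conclusion.** The point holds as a moderate-to-minor defect in a supportive analysis. Section 5.4 as written leads to a conditional odds ratio whose change on adjustment does not show confounding in this randomised trial, and which has no stated route back to the absolute difference of 5.1. The primary conclusion is unaffected.

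The size depends on the true effect and on prognostic strength: none at a true OR of 1; 0.583 to 0.569 with weak covariates (SD 0.5) and to 0.430 with strong ones (SD 2), at 80% versus 70% cure. These figures rest on assumed cure rates, a normal prognostic score and, for the simulation, 150 patients per arm. The SAP states no margin, so none of the differences in points is judged against one here; the protocol may hold it.

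**What to change.** In section 5.4:

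1. Keep logistic regression, but report the adjusted risk difference by marginal standardisation: predict each patient's cure probability under short and under long treatment, average each over all ITT patients in the analysis, and subtract. Give the one-sided 95% interval of 5.1 by the delta method or bootstrap.
2. Present it as a sensitivity analysis beside the unadjusted difference, read against the same criterion.
3. Use a short list of baseline covariates fixed in advance in place of the p < 0.15 screen. Leave out sites grouped by observed cure rate, which are derived from the outcome, and antibiotic group if it is chosen after randomisation (the SAP does not say when it is). Without this step, standardisation would carry unsuitable covariates into the adjusted difference.
4. Delete the check of whether the duration effect is modified on adjustment.

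The cost is a change of SAP wording and a little more code, possibly outside the basic menus of SPSS, the software named in section 4.1. No new data are needed. With prognostic covariates there is also a gain in precision: in the 80% versus 70% simulation the SD of the difference fell from 5.0 to 4.3 points.

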5.2 Secondary endpoints

The secondary endpoints will be collected as dichotomous variables (yes/no) or continuous variables. The ITT, PP and CEP approaches will be used for the analyses of secondary endpoints. The absolute difference with one-side 95% CI proportion will be used for dichotomous variables and absolute difference with one-side 95% CI mean/median (as appropriate) for continuous variables.

5.2.1 Clinical endpoints:

Efficacy of each group of antibiotics used, secondary infections, infection recurrence rate (relapses and reinfections), need for new surgeries (debridement, material removal, covering, amputation), reconstructive surgery strategies (bone

and soft tissue), and functionality of the lower limbs will be reported as proportion. Risk ratios (RRs) and the absolute difference for achieving each endpoint (with 95% CIs), with the long antibiotic treatment arm as the reference group, will be calculated.

Functionality of the upper limbs (Quick-DASH score) and health outcomes (SF-12 or Barthel scores) will be reported as median. The median of each score will be compared between the two treatment groups using parametric or nonparametric tests as appropriate.

5.2.2 Microbiological endpoints: Resistance development to antibiotic used during therapy and *C. difficile* infection during therapy and at 30-day will be reported as proportion. Risk ratios (RRs) and the absolute difference for achieving each endpoint (with 95% CIs), with the long antibiotic treatment arm as the reference group, will be calculated.

5.2.3 Adverse events (AE) and complications: Adverse events and severity, including death (that is, all-cause mortality) will be reported as proportion. Risk ratios (RRs) and the absolute difference for achieving each endpoint (with 95% CIs), with the long antibiotic treatment arm as the reference group, will be calculated.

5.2.4 Consumption of health resources will be evaluated for each type of strategy: days of antibiotic treatment, length of hospital stay, readmissions, and number of surgeries performed will be reported as median. The median of each variable will be compared between the two treatment groups using parametric or nonparametric tests as appropriate.

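### The adjusted model for the duration effect lists antibiotic group as a confounder without fixing it before randomisation; if its use comes to depend on arm, adjusting for it can distort the estimate in either direction (minor: supportive analysis)

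*SAP*

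**What the plan says.** SAP section 1 describes an "open labelled, pragmatic randomized clinical trial comparing different durations of antibiotic therapy". The only blinding to allocation that the SAP describes is that of the outcome committee in section 3.

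Section 5.1 fixes the primary analysis: "The primary analysis will be the absolute difference in the proportion of patients reaching the composited primary outcome variable" cure, in the ITT population. It describes no covariate adjustment.

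Section 5.4 adds a logistic regression. Its entry rule is: "Potential confounders will be identified by bivariate analysis of their associations with the primary outcome, considering a p value <0.15". The selected variables "will be entered into the multivariate model to check if the effect of the duration of therapy is significantly modified". The named candidates are age, Charlson index, delay in DAIR, fracture type and location, and then "type of osteosynthesis material, microorganism, and antibiotic group". The section does not say whether antibiotic group means the planned, first, main or any agent received, or when it is measured.

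Elsewhere the SAP treats the same variable as treatment given: the first clinical secondary endpoint in section 5.2.1 is "Efficacy of each group of antibiotics used".

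**The concern.** Most of the candidates in section 5.4 describe the patient, the injury or the infection. Antibiotic group describes part of the treatment.

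In a randomised comparison, a variable that allocation can affect is not a confounder. An arm difference in it is a consequence of allocation, and conditioning on it can do two kinds of harm:

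- **Part of the effect is removed.** If allocation changes which drugs are used and the drugs differ in efficacy, that difference belongs to the strategy being tested. Adjustment takes it out.
- **A false effect appears.** If drug choice depends on both the arm and unmeasured severity, then within a drug group the two arms no longer have the same mix of severity, even though randomisation balanced it overall.

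The SAP leaves room for this. Treatment is open label. Section 1.1 sets 8 against 12 weeks in early infection, and 12 weeks against treatment continued to union or implant removal in delayed infection. Section 1.4 provides for long-arm patients treated for at least 6 months. If the variable is coded from drugs received, a longer course leaves more time for a switch, so the coding can depend on arm even when the first drug was chosen before allocation.

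At stake is how the model is read. A shift in the adjusted estimate could be taken as evidence against the ITT result, or as support for it, when it only reflects the covariate.

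**Working it through.** The SAP gives no figure on this point, so there is nothing to reproduce. All inputs below are assumptions chosen to show the mechanism. None comes from the documents.

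**1. False effect, no true effect of drug or duration.** Assume severity is split 50/50 in each arm, cure is 90% in milder and 60% in severe patients, drug A is used 40 points more often in milder patients, and overall use of A is 60% (short) v 40% (long). Use of A is then 80% milder and 40% severe in the short arm, and 60% and 20% in the long arm.

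Cure by drug and arm:
- A, short: (0.80×0.90 + 0.40×0.60)/(0.80 + 0.40) = 0.96/1.20 = 80.0%
- A, long: (0.60×0.90 + 0.20×0.60)/(0.60 + 0.20) = 0.66/0.80 = 82.5%
- B, short: (0.20×0.90 + 0.60×0.60)/(0.20 + 0.60) = 0.54/0.80 = 67.5%
- B, long: (0.40×0.90 + 0.80×0.60)/(0.40 + 0.80) = 0.84/1.20 = 70.0%

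Overall cure, short: 0.60×80.0 + 0.40×67.5 = 75.0%. Overall cure, long: 0.40×82.5 + 0.60×70.0 = 75.0%. The true difference is 0, yet within each drug the short arm looks 2.5 points worse. The logistic model of cure on arm and drug gives an odds ratio of 0.87.

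**2. Range.** Same inputs, varying the split by arm and which patients tend to get drug A:

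| Use of A, short v long | A favoured in milder patients: OR (points) | A favoured in severe patients: OR (points) |
|---|---|---|
| 60% v 40% | 0.87 (-2.5) | 1.15 (+2.5) |
| 55% v 45% | 0.94 (-1.2) | 1.07 (+1.2) |
| 52% v 48% | 0.97 (-0.5) | 1.03 (+0.5) |
| 50% v 50% | 1.00 (0) | 1.00 (0) |

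The size follows the dependence on arm, and the sign follows which patients get the drug.

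**3. Effect removed.** Assume cure of 85% with A and 70% with B, and no other effect. At 60% v 40%, cure is 0.60×85 + 0.40×70 = 79% (short) and 0.40×85 + 0.60×70 = 76% (long). The difference is +3.0 points, with OR (0.79/0.21)/(0.76/0.24) = 1.19. With drug in the model the OR is 1.00. The amount removed is the difference in use times 15 points: 0.10×15 = 1.5 points at 55% v 45%, 0.04×15 = 0.6 points at 52% v 48%, and 0 at 50% v 50%.

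**4. Does the p<0.15 screen protect?** It tests association with cure, not timing relative to allocation. In step 1, cure is (0.60×80.0 + 0.40×82.5)/(0.60 + 0.40) = 81% with A and (0.40×67.5 + 0.60×70.0)/(0.40 + 0.60) = 69% with B, although the drug has no effect. A 12-point association is the kind of signal the screen is meant to admit.

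**The case against.** The strongest reply is that the SAP never says the drug is chosen after allocation. It does not give the order of randomisation and drug choice, who chooses, or how antibiotic group is coded. The protocol, which is not at hand, may settle this. If the drug is fixed beforehand, or chosen from the organism alone whatever the arm, there is no bias, as the last row of the table shows. This stands. A reader might infer from the open-label design that clinicians choose the antibiotic knowing the assigned duration. The document does not support that as a fact, and the point does not rest on it. It rests on section 5.4 naming a treatment variable with no restriction to a value before randomisation.

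A second reply is that section 5.4 aims to separate duration from other influences, so an odds ratio of 1.00 in step 3 answers its question: duration does nothing except through the drug. This is fair as far as it goes, and the effect of the strategy as a whole remains available from the primary analysis. It does not cover steps 1 and 2, where the model reports a duration effect that does not exist.

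A third reply is scope. The variable is only a candidate, it enters only if it passes the screen, and the SAP ties no non-inferiority decision to this model. This also stands, and it limits the severity.

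**Conclusion.** The point holds in conditional form. As written, section 5.4 permits adjustment for a variable that allocation can affect. If the distribution of antibiotic group depends on arm, the adjusted duration effect can be distorted in either direction. Under the assumed inputs the distortion runs from none to about 2.5 points in the false-effect case, and from none to 3.0 points in the removed-effect case. Larger dependence on arm would give more.

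Two stronger readings are not supported. The documents do not show that drug choice does depend on arm, so bias cannot be asserted. Nor is the trial's main conclusion at risk on this ground, because the primary ITT difference in section 5.1 is unadjusted. Severity is minor, limited to a supportive analysis.

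**What to change.** In section 5.4, state that covariates are limited to variables fixed before randomisation, and remove antibiotic group from the list. As an alternative, and only if it was recorded at that time, use the antibiotic class being given before the allocation was known. Report the antibiotics received by arm as a description of treatment.

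The cost is about one sentence. Removing the term needs no new data; the alternative does need the class to have been recorded before allocation, which the SAP does not show. The downside is a small possible loss of precision if drug class is strongly prognostic and independent of arm. If the drug is in fact always fixed before randomisation, saying so in section 5.4 closes the ambiguity.
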